11.5.3 Vital Signs

Vital Signs will be recorded at Screening, Cycle 1 [Day 1, Day 2, Day 8, Day 15], cycle 2 [Day 1, Day 8, Day 15], Cycle X [Day 1, Day 8, Day 15], End of treatment and Follow-up visit.

Vital signs parameters (systolic and diastolic blood pressure, pulse rate, respiratory rate and temperature) will be summarised and listed using the SAF.

11.5.4 Electrocardiogram

Single 12-lead ECGs will be performed at Screening, Cycle 1 [Day 1, Day 2, Day 8, Day 15], cycle 2 [Day 1], Cycle X Day 1 and End of treatment visit.

Single 12-lead ECG parameters (heart rate, PR interval, QRS, QT interval, QT interval corrected using Fridericia's formula (QTcF)) will be summarised using a shift table and listed using the SAF.

11.5.5 Physical Examination

Physical examination will be performed at Screening, Cycle 1 [Day 1, Day 2, Day 8, Day 15], Cycle 2 [Day 1, Day 2 and Day 15], Cycle X [Day 1, Day 2 and Day 15] and End of treatment visit.

Physical examination (Normal, Abnormal Clinically Significant and Abnormal Not Clinically Significant) will be summarised and listed using the SAF.

11.5.6 ECOG

ECOG will be performed at Screening, Cycle 1 Day 1, Cycle 2 Day 1, Cycle X Day 1, End of treatment and Follow-up visit.

ECOG status will be summarised and listed using the SAF.

11.6 OTHER DATA

Data related to the following will be presented if required:

- Medical history
- Oncology history
- CT/MRI
- Tumour biopsies

11.6.1 Prior and Concomitant Medication

All prior and concomitant medications will be classified using the World Health Organisation Drug Dictionary (WHODD) coding dictionary (version as documented within the DMP) and listed using the ATC Level 4 class, Preferred Term and verbatim text.

Any administered medication will be assigned as concomitant if it starts on or after first IMP use or ends after first IMP use regardless of start date. Any medication that stops prior to first IMP use will be assigned as prior medication.

Where there are only partial dates/times recorded for a medication, the medication will be assigned as concomitant if it cannot be ruled out it is concomitant based on the partial information.

Prior and concomitant medications will be listed by period/regimen using the Safety Set (SAF).

Derivations within listings:

Analysis sets: Detail whether subject should be included within each of the analysis sets and provide reason for exclusion, as appropriate.

Inclusion/Exclusion criteria: Only failures to be presented. If there are no failures display '*All subjects passed all inclusion/exclusion criteria.*'

Protocol deviations: Major/minor classification to be assigned and confirmed by Sponsor.

12 VALIDATION

All datasets, tables, figures and listings will be subject to independent quality control and visual review. Datasets and tables will be independently double-programmed, figures and listings subject to spot checks and visual QC.

14 LIST OF TABLES, FIGURES AND LISTINGS

List of Tables and Figures Contained in Report Section 14

14.1 Disposition and Demographic Data

14.1.1 Disposition Data

Table 14.1.1.1	Summary of Study Disposition	All Patients Set
----------------	------------------------------	------------------

14.1.2 Demographic Data and Baseline Characteristics

Table 14.1.2.1	Summary of Demographic and Baseline Information	Safety Set
Table 14.1.2.2	Summary of Demographic and Baseline Information	Full Analysis Set

14.2 Efficacy Data

14.2.1 Efficacy parameters

Table 14.2.1.1	Summary of PFS	Safety Set
Table 14.2.1.2	Summary of PFS	Full Analysis Set
Table 14.2.1.3	Summary of PFS	Per Protocol Set <Part 2 only>
Table 14.2.2.1	Summary of Efficacy parameters, DCR, ORR, OS, TTP, TTR and DOR	Safety Set
Table 14.2.2.2	Summary of Efficacy parameters, DCR, ORR, OS, TTP, TTR and DOR	Full Analysis Set
Table 14.2.2.3	Summary of Efficacy parameters, DCR, ORR, OS, TTP, TTR and DOR	Per Protocol Set <Part 2 only>
Table 14.2.5	Dosing of OMO 103-01	Safety Set
Table 14.2.6	Change from Baseline: Quality of Life Questionnaire	Safety Set
Figure 14.2.6.1	Kaplan-Meier Plot of Time from Start of IMP to TTP	Full Analysis Set
Figure 14.2.6.2	Kaplan-Meier Plot of Time from Start of IMP to TTP	Per Protocol Set <Part 2 only>
Figure 14.2.7.1	Kaplan-Meier Plot of Time from Start of IMP to TTR	Full Analysis Set
Figure 14.2.7.2	Kaplan-Meier Plot of Time from Start of IMP to TTR	Per Protocol Set <Part 2 only>

I4.3 Safety Data**I4.3.1 Adverse Events**

Table I4.3.1.1	Summary of Treatment Emergent Adverse Events	Safety Set
Table I4.3.1.1a	Summary of Treatment Emergent Adverse Events – Event Count	Safety Set
Table I4.3.1.2	Summary of Treatment Emergent Adverse Events by System Organ Class and Preferred Term	Safety Set
Table I4.3.1.2a	Summary of Treatment Emergent Adverse Events by System Organ Class and Preferred Term – Event Count	Safety Set
Table I4.3.1.3	Summary of Treatment Emergent Adverse Events by Preferred Term	Safety Set
Table I4.3.1.4	Summary of Treatment Emergent Adverse Events by Severity, System Organ Class and Preferred Term	Safety Set
Table I4.3.1.5	Summary of Treatment Emergent Adverse Events by Relationship to IMP, System Organ Class and Preferred Term	Safety Set
Table I4.3.1.6	Serious Adverse Events	Safety Set
Table I4.3.1.7	Adverse Events Leading to Withdrawal	Safety Set

I4.3.2 Laboratory Safety

Table I4.3.2.1	Biochemistry Out of Normal Range Data	Safety Set
Table I4.3.2.2	Haematology Out of Normal Range Data	Safety Set
Table I4.3.2.3	Urinalysis Abnormal Values	Safety Set
Table I4.3.2.4	Autoimmune Values	Safety Set
Table I4.3.2.5	Frequency of Autoimmune Values	Safety Set

I4.3.3 ECG Data

Table I4.3.3.1	Statistical summaries of ECG parameters by visit	Safety Set
----------------	--	------------

I4.3.4 ECOG Performance Status

Table I4.3.4.1	Statistical summaries of ECOG status by visit	Safety Set
----------------	---	------------

I4.3.5 Vital Signs

Table I4.3.5.1	Statistical summaries of Vital Signs by visit	Safety Set
----------------	---	------------

I4.3.6 Physical Examination

Table I4.3.6.1	Statistical summaries of Physical Examination by visit	Safety Set
----------------	--	------------

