15 SHELLS FOR TABLES, FIGURES AND LISTINGS

The intended layouts for tables, figures and listings are presented. However, it may be appropriate to change the layouts, upon review of the data available, for completeness and clarity.

QCd output will be produced as Rich Text Format (.rtf) files for convenient inclusion in the CSR. The default tables, figures and listings (TFL) layout will be as follows:

Orientation	A4 Landscape								
Margins	
 
 Top:	2.54 cm	
 
 Bottom:	2.54 cm	
 
 Left:	2.54 cm	
 
 Right:	2.54 cm	
 
	Top:	2.54 cm	Bottom:	2.54 cm	Left:	2.54 cm	Right:	2.54 cm
Top:	2.54 cm								
Bottom:	2.54 cm								
Left:	2.54 cm								
Right:	2.54 cm								
Font	Courier New 9pt								
Headers (Centre)	Sponsor Protocol Number, TFL Number, Title, Analysis Set								
Footers (Left)	Source Listing, Date/Time TFL Generated, Page Number, i.e. Page x of y								

Listing shells are displayed within this document without the comments field but, should there be any comments recorded for the represented data, this field will be added to the listing. In addition, at the time of programming, footnotes will be added to the listing, table or figure as needed. All footnotes will be used for purposes of clarifying the presentation

Should the number of variables within a listing or table be too great to fit on one page without compromising clarity, then the variables will be split across multiple subsequent pages and key identifying variables replicated with these (i.e. subject number, visit etc). The differing pages will be identified using a sequential number which will follow the TFL title, i.e. xxxx - (1), xxxx - (2).

OMO-103-01
Table 14.1.1.1
Summary of Study Disposition - Part 1
All Patients Set

	Number of Subjects (%)
Consented	x
Screening Failures/Non-Runners	x
Dosed:	
0.48 mg/kg (Cohort 1)	x (x.x)
1.44 mg/kg (Cohort 2)	x (x.x)
.....	x (x.x)
Completed Study	x (x.x)
Early Withdrawal	x (x.x)
Reason for Early Withdrawal	
ADVERSE EVENT	x (x.x)
LOST TO FOLLOW-UP	x (x.x)
WITHDRAWAL BY SUBJECT	x (x.x)
STUDY TERMINATED BY SPONSOR	x (x.x)
PHYSICIAN DECISION	x (x.x)
PREGNANCY	x (x.x)
PROTOCOL VIOLATION	x (x.x)
DEATH	x (x.x)
OTHER	x (x.x)
Safety Set	x (x.x)
Full Analysis Set	x (x.x)
Per Protocol Set	x (x.x)

Source Listing: 16.2.1.2, 16.2.3.1; Produced: yyyy-mm-ddThh:mm - Page x of y
Percentages are based on the total number of dosed subjects.

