		Complete Response	N	x
		Partial Response	N	x
	Overall (N=x)	DCR	Ratio (%)	x.x %
		Complete Response	N	x
		Partial Response	N	x
Stable Disease		N	x	
ORR.....				
TTP	Cohort 1 (Dose 0.48 mg/kg) (N=x)		N	X
			Mean	x.x
			SD	x.xxx
			Min	x

Parameter	Cohort	Component	Statistics	Result
			Median	x.x
			Max	X
TTR...	...			
DOR				

Source Listing: 16.2.7.2; Produced: yyyy-mm-ddThh:mm - Page x of y
Percentages are based on the total number of subjects within the Safety Set

*Programming note: A similar table will be presented for Table 14.2.2.2 (FAS) and Table 14.2.2.3 (PPS - Part 2 only)
Recommend one page be given to each of the 6 parameters (then repeated for 3 populations as above)
A similar table will be presented for Part 2 with Overall Survival (OS) included.*

OMO-103-01
Table 14.2.5
Dosing of OMO 103-101 - Part 1
Safety Set

Cohort	Statistic	
Cohort 1	n	x
	Mean	x.x
	SD	x.xx
	Min	x
	Median	x.x
	Max	x
Cohort 2	n	x
	Mean	x.x
	SD	x.xx
	Min	x
	Median	x.x
	Max	x
.....		

Source Listing: 16.2.5.1; Produced: yyyy-mm-ddThh:mm - Page x of y
Percentages are based on the total number of subjects within the Safety Set.

Programming note: A similar table will be presented (within the same table number) for Part 2 Dosing

OMO-103-01
Table 14.2.6
Change from Baseline: Quality of Life Questionnaire - Part 1
Safety Set

<Question's group> (Physical, Emotional, Fatigue, Global)

		COHORT 1 (Dose xx mg/ml) (N=x)	COHORT 2 (Dose xx mg/ml) (N=x)	...	Overall (N=xx)
Baseline	n	xx (xx.x %)	xx (xx.x %)		xx (xx.x %)
	Mean	xx.xx	xx.xx		xx.xx
	SD	xx.xx	xx.xx		xx.xx
	Minimum	xx.x	xx.x		xx.x
	Maximum	xx.x	xx.x		xx.x
	Median	xx.xx	xx.x		xx.xx
Visit	n	xx (xx.x %)	xx (xx.x %)		xx (xx.x %)
	Mean	xx.xx	xx.xx		xx.xx
	Etc				
Change from Baseline to Visit	n	xx (xx.x %)	xx (xx.x %)		xx (xx.x %)
	Mean	xx.xx	xx.xx		xx.xx
	Etc				
Etc					

Source Listing: 16.2.7.5; Produced: yyyy-mm-ddThh:mm - Page x of y
 The denominator for each percentage is the number of patients within the column.
 Physical functioning = sum of Q1, Q2, Q3, Q4 and Q5 scores.
 Emotional functioning = sum of Q21, Q22, Q23, and Q24 scores.
 Fatigue = sum of Q10, Q12 and Q18 scores.
 Global = sum of Q29 and Q30.

Programming note: A similar table will be presented for Part 2.

OMO-103-01
Figure 14.2.6.1
Kaplan-Meier Plot of Time from Start of IMP to TTP
Full Analysis Set

Figure Specifications

Procedure: PROC LIFETEST - survival plot

By: Treatment

x axis: Time

x axis: Label: Time Post-Dose (h)

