x axis: values: As appropriate

Y axis: Survival proportion

Y axis Label: Proportion without TTP

Y axis values: As appropriate

Legend:

(dose) OMO 103-101 (N=X) - linestyle = solid, colour = blue

The number of subjects at risk should be presented (option plots=survival(asterisk)).

Source Listing: 16.2.7.2; Produced: yyyy-mm-ddThh:mm - Page x of y
Censoring occurs where a subject did not record TTP within the study.

This layout also applies to:

Figures 14.2.6.2 (Repeat of above for PPS), 14.2.7.1 (Repeat of above for TTR), 14.2.7.2 (Repeat of 14.2.7.2 for PPS)

OMO-103-01
Table 14.3.1.1
Summary of Treatment Emergent Adverse Events - Part 1
Safety Set

	COHORT 1 (Dose xx mg/ml) (N=x)	COHORT 2 (Dose xx mg/ml) (N=x)	Overall (N=x)
Number (%) of subjects with TEAE by grade and relationship to study drug:				
GRADE 1	x (x.x)	x (x.x)	x (x.x)	x (x.x)
NOT RELATED	x (x.x)	x (x.x)	x (x.x)	x (x.x)
POSSIBLY RELATED	x (x.x)	x (x.x)	x (x.x)	x (x.x)
RELATED	x (x.x)	x (x.x)	x (x.x)	x (x.x)
GRADE 2	x (x.x)	x (x.x)	x (x.x)	x (x.x)
NOT RELATED	x (x.x)	x (x.x)	x (x.x)	x (x.x)
POSSIBLY RELATED	x (x.x)	x (x.x)	x (x.x)	x (x.x)
RELATED	x (x.x)	x (x.x)	x (x.x)	x (x.x)
GRADE ...	x (x.x)	x (x.x)	x (x.x)	x (x.x)

Source Listing: 16.2.8.1; Produced: yyyy-mm-ddThh:mm - Page x of y

A subject with multiple adverse events is counted only once at the maximum level of severity or the strongest relationship to study drug.

Percentages will be calculated from the number of subjects in the Safety Set within a cohort.

Programming note: A similar table will be presented for Part 2, with the column headers for each of the 3 groups. A similar table will be presented for Table 14.3.1.1a replacing patient counts by AE event counts.

OMO-103-01
Table 14.3.1.2
Summary of Treatment Emergent Adverse Events by System Organ Class and Preferred Term - Part 1
Safety Set

System Organ Class Preferred Term	Number of Events / Subjects (%)			
	COHORT 1 (Dose xx mg/ml) (N=x)	COHORT 2 (Dose xx mg/ml) (N=x)	Overall (N=x)
Any TEAEs	x / x (x.x)	x / x (x.x)	x / x (x.x)	x / x (x.x)
<SYSTEM ORGAN CLASS TERM> <PREFERRED TERM> <PREFERRED TERM>	x / x (x.x) x / x (x.x)	x / x (x.x) x / x (x.x)	x / x (x.x) x / x (x.x)	x / x (x.x) x / x (x.x)

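### The planned Kaplan-Meier plots of time to response show more response than was observed if patients who progress or die without responding are censored before a later response

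*SAP*

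**What the plan says.** SAP section 14.2.1 lists Figure 14.2.7.1 (FAS) and Figure 14.2.7.2 (PPS, Part 2 only), both titled "Kaplan-Meier Plot of Time from Start of IMP to TTR". Section 11.3 calls for Kaplan-Meier plots of time-to-event endpoints and treats all efficacy endpoints descriptively.

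TTR has no shell of its own. Section 15 specifies Figure 14.2.6.1 for TTP, and the layout note beneath it extends that design: "14.2.7.1 (Repeat of above for TTR". The inherited specification is:

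- method: "Procedure: PROC LIFETEST - survival plot";
- axis: "Y axis Label: Proportion without TTP";
- risk table: "The number of subjects at risk should be presented";
- censoring footnote: "Censoring occurs where a subject did not record TTP within the study".

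The footnote says who is censored, not at what date, and it is worded for TTP.

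Section 6.3 admits to the FAS anyone in the Safety Set with a primary or secondary endpoint recorded. Section 6.5 restricts the PPS to FAS subjects who complete the study without a relevant major deviation. Neither set requires a response. ORR for the same sets appears in Tables 14.2.2.2 (FAS) and 14.2.2.3 (PPS), titled "Summary of Efficacy parameters, DCR, ORR, OS, TTP, TTR and DOR".

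**The concern.** For TTP, progression is the event. For TTR, progression or death without a response is what ends the patient's chance of an on-study response. A shell written for the first endpoint does not carry over to the second without saying how such patients are handled.

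Kaplan-Meier treats a censored patient as someone who could still respond at the same rate as those left at risk. If non-responders are removed when they progress or die, each later response is divided by a shrunken risk set and the curve drops too far. A reader who takes one minus the curve as the chance of response would then get a higher figure than the ORR table gives for the same set, inside one report. What is at stake is how the figure is read. The ORR estimate itself is not affected.

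**Working it through.** The documents state no figure for this curve, so there is none to reproduce. The check has two parts.

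**Who enters as censored.** A product-limit curve has only two outcomes, event or censored.

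- FAS: membership does not depend on response, and no competing-risk method is named. Patients who progress or die without a response are therefore censored observations.
- PPS: progression is not a named withdrawal reason in the disposition shell (Table 14.1.1.1), so progressors who complete the study can be in this set and are censored in the same way. That shell contrasts completion with early withdrawal and lists death as a withdrawal reason. Patients who die on study may therefore be excluded from the PPS by the completion requirement.

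**What the censoring date does.** The group size of 18 is the planned Part 2 group size (protocol synopsis, sample size; SAP section 3.4). All response and exit counts are assumptions: one response at scan 1, one at scan 2, and *p* non-responders censored at scan 1 but still counted at risk for that scan.

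- Observed response: 2/18 = 11.1%.
- At risk at scan 2: 18 − 1 − *p* = 17 − *p*.
- One minus Kaplan-Meier: 1 − (17/18) × (1 − 1/(17 − *p*)).
- Cumulative incidence with the *p* exits as competing events: 1/18 + ((17 − *p*)/18) × (1/(17 − *p*)) = 2/18.

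| *p* | At risk, scan 2 | 1 − KM | Result | Ratio to observed | Cumulative incidence |
|---|---|---|---|---|---|
| 0 | 17 | 1 − (17/18)(16/17) | 11.1% | 1.00 | 11.1% |
| 3 | 14 | 1 − (17/18)(13/14) | 12.3% | 1.11 | 11.1% |
| 6 | 11 | 1 − (17/18)(10/11) | 14.1% | 1.27 | 11.1% |
| 9 | 8 | 1 − (17/18)(7/8) | 17.4% | 1.56 | 11.1% |
| 12 | 5 | 1 − (17/18)(4/5) | 24.4% | 2.20 | 11.1% |

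Two conditions remove the excess:

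- Non-responders stay at risk until after the last response. This is the *p* = 0 row, whatever the number who progress.
- Both responses occur at scan 1 and nobody leaves earlier. Then 1 − 16/18 = 11.1%, even with nine patients progressing at that same scan.

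Pooling the three groups to 54 and tripling every count gives the same percentages by construction, so it adds no separate evidence.

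**The case against.** The strongest reply is that the harm needs two conditions: non-responders must be censored before a later response, and a reader must invert a curve labelled as the proportion without the event. Carried over to TTR, the footnote's reference to the event not being recorded within the study is compatible with keeping living progressors at risk through follow-up, which would reduce or remove the excess. This stands, and it is why the point is conditional.

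Second, the handling may be defined elsewhere. SAP section 1.1 says the plan is to be read with the protocol, and the protocol text available here is the synopsis. Section 15 also says that "at the time of programming, footnotes will be added to the listing, table or figure as needed". This stands as a limit. A footnote stating a censoring date would settle the ambiguity, but a date at progression or death would still produce the excess, so the choice of method matters as well as the wording.

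Third, the consequence is small. ORR is tabulated for the same sets, numbers at risk are printed, and the Part 2 interim rule in section 8 uses observed responses. This stands in full.

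A reader might infer that the plan will overstate the response rate, or that every death in both sets becomes a censored observation. The documents support neither. The available text does not fix the censoring date, ORR is not derived from this curve, and on-study deaths may not be in the PPS at all.

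**Conclusion.** The point holds in conditional form and is minor. Kaplan-Meier is the stated method for TTR in sets not restricted to responders, and the available text leaves the censoring date open. If patients who progress or die without a response (in the PPS, at least the progressors) are censored before a later response, one minus the curve exceeds the observed response rate for that set. Otherwise it does not.

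The size cannot be fixed from the documents, which give no response rate, attrition or timing. In the illustration the ratio to the observed rate runs from 1.00 to 2.20. It rests on two responses split across two scans in one Part 2 group. Figure 14.2.7.1 is not confined to Part 2, and the small Part 1 cohorts are not modelled here. No test, stopping rule or primary endpoint depends on the curve.

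**What to change.** Replace Figures 14.2.7.1 and 14.2.7.2 with cumulative incidence (Aalen-Johansen) plots of response, keep the numbers at risk, label the axis as cumulative incidence of response, and replace the TTP footnote with:

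*Event: first response by RECIST v1.1, using the same response definition as ORR. Competing event: progression or death without a prior response. All other patients without a response, including those who withdraw, are lost to follow-up or stop treatment before progression, are censored at the last evaluable tumour assessment.*

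The curve then ends at the ORR only if the two response definitions match and nobody is censored before the last response. If the full protocol already defines TTR censoring, align the footnote with it. Correct the layout note at the same time, since it describes Figure 14.2.7.2 as a repeat of itself.

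Alternatively, drop both figures and summarise TTR in responders only (n, median, range) beside ORR in Tables 14.2.2.2 and 14.2.2.3.

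The cost is a small shell and programming change on data already collected. Dropping the figures loses the picture of response timing.

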14.4 Pharmacokinetics

No pk analysis will be perform by Simbec-Orion.

14.5 Pharmacodynamics

No pd analysis will be perform by Simbec-Orion.

Subject Data: Listings Contained in Report Appendix 16.2**16.2.1 Visit Dates, Dosing Information and Disposition**

Listing 16.2.1.1	Visit Dates	Safety Set
Listing 16.2.1.2	Subject Disposition	All Patients Set

16.2.2 Protocol Deviations

Listing 16.2.2.1	Protocol Deviations	Safety Set
------------------	---------------------	------------

16.2.3 Analysis Sets

Listing 16.2.3.1	Analysis Sets	All Patients Set
------------------	---------------	------------------

16.2.4 Demographic Data and Other Baseline Characteristics

Listing 16.2.4.1	Demographic Information	Safety Set
Listing 16.2.4.2	Medical History	Safety Set
Listing 16.2.4.3	Inclusion/Exclusion Criteria Failures	Safety Set

16.2.5 Dosing

Listing 16.2.5.1	Summary of OMO 103-01 dosing	Safety Set
------------------	------------------------------	------------

16.2.7 Efficacy

Listing 16.2.7.1	Summary of PFS	Safety Set
Listing 16.2.7.2	Summary of Efficacy parameters, DCR, ORR, OS, TTP, TTR and DOR	Safety Set
Listing 16.2.7.3	Summary of biomarkers	Safety Set
Listing 16.2.7.5	QoL Questionnaire	Safety Set

16.2.8 Adverse Events

Listing 16.2.8.1	Adverse Events	Safety Set
------------------	----------------	------------

16.2.9 Individual Laboratory Safety Measurements

Listing 16.2.9.1	Biochemistry Data	Safety Set
Listing 16.2.9.2	Haematology Data	Safety Set
Listing 16.2.9.3	Urinalysis Data	Safety Set
Listing 16.2.9.4	Summary of Anti-drug antibodies (ADA) to OMO-103	Safety Set
Listing 16.2.9.5	Other Laboratory Data	Safety Set

16.2.10 Vital Signs

Listing 16.2.10.1	Vital Signs Data	Safety Set
-------------------	------------------	------------

16.2.11 Physical Examination

Listing 16.2.11.1	Physical Examination Data	Safety Set
-------------------	---------------------------	------------

16.2.12 ECG

Listing 16.2.12.1	Single 12-lead ECG Data	Safety Set
-------------------	-------------------------	------------

16.2.13 Prior and Concomitant Medication

Listing 16.2.13.1	Prior Medications	Safety Set
Listing 16.2.13.2	Concomitant Medications	Safety Set

16.2.15 ECOG scores

Listing 16.2.15.1	ECOG scores	Safety Set
-------------------	-------------	------------

15 SHELLS FOR TABLES, FIGURES AND LISTINGS

The intended layouts for tables, figures and listings are presented. However, it may be appropriate to change the layouts, upon review of the data available, for completeness and clarity.

QCd output will be produced as Rich Text Format (.rtf) files for convenient inclusion in the CSR. The default tables, figures and listings (TFL) layout will be as follows:

Orientation	A4 Landscape								
Margins	
 
 Top:	2.54 cm	
 
 Bottom:	2.54 cm	
 
 Left:	2.54 cm	
 
 Right:	2.54 cm	
 
	Top:	2.54 cm	Bottom:	2.54 cm	Left:	2.54 cm	Right:	2.54 cm
Top:	2.54 cm								
Bottom:	2.54 cm								
Left:	2.54 cm								
Right:	2.54 cm								
Font	Courier New 9pt								
Headers (Centre)	Sponsor Protocol Number, TFL Number, Title, Analysis Set								
Footers (Left)	Source Listing, Date/Time TFL Generated, Page Number, i.e. Page x of y								

Listing shells are displayed within this document without the comments field but, should there be any comments recorded for the represented data, this field will be added to the listing. In addition, at the time of programming, footnotes will be added to the listing, table or figure as needed. All footnotes will be used for purposes of clarifying the presentation

Should the number of variables within a listing or table be too great to fit on one page without compromising clarity, then the variables will be split across multiple subsequent pages and key identifying variables replicated with these (i.e. subject number, visit etc). The differing pages will be identified using a sequential number which will follow the TFL title, i.e. xxxx - (1), xxxx - (2).

OMO-103-01
Table 14.1.1.1
Summary of Study Disposition - Part 1
All Patients Set

	Number of Subjects (%)
Consented	x
Screening Failures/Non-Runners	x
Dosed:	
0.48 mg/kg (Cohort 1)	x (x.x)
1.44 mg/kg (Cohort 2)	x (x.x)
.....	x (x.x)
Completed Study	x (x.x)
Early Withdrawal	x (x.x)
Reason for Early Withdrawal	
ADVERSE EVENT	x (x.x)
LOST TO FOLLOW-UP	x (x.x)
WITHDRAWAL BY SUBJECT	x (x.x)
STUDY TERMINATED BY SPONSOR	x (x.x)
PHYSICIAN DECISION	x (x.x)
PREGNANCY	x (x.x)
PROTOCOL VIOLATION	x (x.x)
DEATH	x (x.x)
OTHER	x (x.x)
Safety Set	x (x.x)
Full Analysis Set	x (x.x)
Per Protocol Set	x (x.x)

Source Listing: 16.2.1.2, 16.2.3.1; Produced: yyyy-mm-ddThh:mm - Page x of y
Percentages are based on the total number of dosed subjects.

Programming note: A similar table will be presented for Part 2 (Dose expansion)

OMO-103-01
Table 14.1.2.1
Summary of Demographic and Baseline Information - Part 1
Safety Set

Parameter	Statistic	All Subjects (N=x)
Age (yrs)	n	x
	Mean	x.x
	SD	x.xx
	Min	x
	Median	x.x
	Max	x
Height (cm)	n	x
	Mean	x.x
	SD	x.xx
	Min	x
	Median	x.x
	Max	x
Weight (kg)	n	x
	Mean	x.xx
	SD	x.xxx
	Min	x.x
	Median	x.xx
	Max	x.x
Number of pre-treatments per patient	n	x
	Mean	x.xx
	SD	x.xxx
	Min	x.x
	Median	x.xx
	Max	x.x

Source Listing: 16.2.4.1; Produced: yyyy-mm-ddThh:mm - Page x of y

Percentages are based on the total number of subjects within the Safety Set.

Programming note: A similar table will be presented for Part 2.

[Continued overleaf...]

OMO-103-01
Table 14.1.2.1
Summary of Demographic and Baseline Information - Part 1
Safety Set

Parameter		Statistic	All Subjects (N=x)
Race:	BLACK OR AFRICAN AMERICAN	n (%)	x (x.x)
	AMERICAN INDIAN OR ALASKA NATIVE	n (%)	x (x.x)
	ASIAN	n (%)	x (x.x)
	NATIVE HAWAIIAN OR OTHER PACIFIC ISLANDER	n (%)	x (x.x)
	WHITE	n (%)	x (x.x)
	MIXED	n (%)	x (x.x)
	OTHER	n (%)	x (x.x)
Gender:	M	n (%)	x (x.x)
	F	n (%)	x (x.x)

Source Listing: 16.2.4.1; Produced: yyyy-mm-ddThh:mm - Page x of y
Percentages are based on the total number of subjects within the Safety Set.

*Programming note: A similar table will be repeated for 14.1.2.2 (FAS).
A similar table will be presented for Part 2.*

OMO-103-01
Table 14.2.1.1
Summary of Progression Free Survival (PFS) - Part 1
Safety Set

Parameter	Cohort	Statistic	
PFS	Cohort 1 (Dose 0.48 mg/kg) (N=x)	n	x
		Mean	x.x
		SD	x.xx
		Min	x
		Median	x.x
		Max	x
	Cohort 2 (Dose 1.44 mg/kg) (N=x)	n	x
		Mean	x.x
		SD	x.xx
		Min	x
		Median	x.x
		Max	x
	Cohort ...		
	Overall (N=x)	n	x
		Mean	x.x
		SD	x.xx
		Min	x
		Median	x.x
Max		x	

Source Listing: 16.2.7.1; Produced: yyyy-mm-ddThh:mm - Page x of y
Percentages are based on the total number of subjects within the Safety Set.

*Programming note: A similar table will be presented for Table 14.2.1.2 (FAS) and Table 14.2.1.3 (PPS)
All tables will be repeated for Part 2.*

OMO-103-01
Table 14.2.2.1
Summary of Efficacy parameters, DCR, ORR, TTP, TTR and DOR - Part 1
Safety Set

Parameter	Cohort	Component	Statistics	Result
DCR	Cohort 1 (Dose 0.48 mg/kg) (N=x)	DCR	Ratio (%)	x.x %
		Complete Response	N	x
		Partial Response	N	x
	Cohort 2 (Dose 1.44 mg/kg) (N=x)	DCR	Ratio (%)	x.x %
		Complete Response	N	x
		Partial Response	N	x
	Cohort 2 Escalation ...	DCR	Ratio (%)	x.x %
		Complete Response	N	x
		Partial Response	N	x
	Overall (N=x)	DCR	Ratio (%)	x.x %
		Complete Response	N	x
		Partial Response	N	x
Stable Disease		N	x	
ORR.....				
TTP	Cohort 1 (Dose 0.48 mg/kg) (N=x)		N	X
			Mean	x.x
			SD	x.xxx
			Min	x

Parameter	Cohort	Component	Statistics	Result
			Median	x.x
			Max	X
TTR...	...			
DOR				

Source Listing: 16.2.7.2; Produced: yyyy-mm-ddThh:mm - Page x of y
Percentages are based on the total number of subjects within the Safety Set

*Programming note: A similar table will be presented for Table 14.2.2.2 (FAS) and Table 14.2.2.3 (PPS - Part 2 only)
Recommend one page be given to each of the 6 parameters (then repeated for 3 populations as above)
A similar table will be presented for Part 2 with Overall Survival (OS) included.*

OMO-103-01
Table 14.2.5
Dosing of OMO 103-101 - Part 1
Safety Set

Cohort	Statistic	
Cohort 1	n	x
	Mean	x.x
	SD	x.xx
	Min	x
	Median	x.x
	Max	x
Cohort 2	n	x
	Mean	x.x
	SD	x.xx
	Min	x
	Median	x.x
	Max	x
.....		

Source Listing: 16.2.5.1; Produced: yyyy-mm-ddThh:mm - Page x of y
Percentages are based on the total number of subjects within the Safety Set.

Programming note: A similar table will be presented (within the same table number) for Part 2 Dosing

OMO-103-01
Table 14.2.6
Change from Baseline: Quality of Life Questionnaire - Part 1
Safety Set

<Question's group> (Physical, Emotional, Fatigue, Global)

		COHORT 1 (Dose xx mg/ml) (N=x)	COHORT 2 (Dose xx mg/ml) (N=x)	...	Overall (N=xx)
Baseline	n	xx (xx.x %)	xx (xx.x %)		xx (xx.x %)
	Mean	xx.xx	xx.xx		xx.xx
	SD	xx.xx	xx.xx		xx.xx
	Minimum	xx.x	xx.x		xx.x
	Maximum	xx.x	xx.x		xx.x
	Median	xx.xx	xx.x		xx.xx
Visit	n	xx (xx.x %)	xx (xx.x %)		xx (xx.x %)
	Mean	xx.xx	xx.xx		xx.xx
	Etc				
Change from Baseline to Visit	n	xx (xx.x %)	xx (xx.x %)		xx (xx.x %)
	Mean	xx.xx	xx.xx		xx.xx
	Etc				
Etc					

Source Listing: 16.2.7.5; Produced: yyyy-mm-ddThh:mm - Page x of y
 The denominator for each percentage is the number of patients within the column.
 Physical functioning = sum of Q1, Q2, Q3, Q4 and Q5 scores.
 Emotional functioning = sum of Q21, Q22, Q23, and Q24 scores.
 Fatigue = sum of Q10, Q12 and Q18 scores.
 Global = sum of Q29 and Q30.

Programming note: A similar table will be presented for Part 2.

OMO-103-01
Figure 14.2.6.1
Kaplan-Meier Plot of Time from Start of IMP to TTP
Full Analysis Set

Figure Specifications

Procedure: PROC LIFETEST - survival plot

By: Treatment

x axis: Time

x axis: Label: Time Post-Dose (h)

x axis: values: As appropriate

Y axis: Survival proportion

Y axis Label: Proportion without TTP

Y axis values: As appropriate

Legend:

(dose) OMO 103-101 (N=X) - linestyle = solid, colour = blue

The number of subjects at risk should be presented (option plots=survival(asterisk)).

Source Listing: 16.2.7.2; Produced: yyyy-mm-ddThh:mm - Page x of y
Censoring occurs where a subject did not record TTP within the study.

This layout also applies to:

Figures 14.2.6.2 (Repeat of above for PPS), 14.2.7.1 (Repeat of above for TTR), 14.2.7.2 (Repeat of 14.2.7.2 for PPS)

OMO-103-01
Table 14.3.1.1
Summary of Treatment Emergent Adverse Events - Part 1
Safety Set

	COHORT 1 (Dose xx mg/ml) (N=x)	COHORT 2 (Dose xx mg/ml) (N=x)	Overall (N=x)
Number (%) of subjects with TEAE by grade and relationship to study drug:				
GRADE 1	x (x.x)	x (x.x)	x (x.x)	x (x.x)
NOT RELATED	x (x.x)	x (x.x)	x (x.x)	x (x.x)
POSSIBLY RELATED	x (x.x)	x (x.x)	x (x.x)	x (x.x)
RELATED	x (x.x)	x (x.x)	x (x.x)	x (x.x)
GRADE 2	x (x.x)	x (x.x)	x (x.x)	x (x.x)
NOT RELATED	x (x.x)	x (x.x)	x (x.x)	x (x.x)
POSSIBLY RELATED	x (x.x)	x (x.x)	x (x.x)	x (x.x)
RELATED	x (x.x)	x (x.x)	x (x.x)	x (x.x)
GRADE ...	x (x.x)	x (x.x)	x (x.x)	x (x.x)

Source Listing: 16.2.8.1; Produced: yyyy-mm-ddThh:mm - Page x of y

A subject with multiple adverse events is counted only once at the maximum level of severity or the strongest relationship to study drug.

Percentages will be calculated from the number of subjects in the Safety Set within a cohort.

Programming note: A similar table will be presented for Part 2, with the column headers for each of the 3 groups. A similar table will be presented for Table 14.3.1.1a replacing patient counts by AE event counts.

OMO-103-01
Table 14.3.1.2
Summary of Treatment Emergent Adverse Events by System Organ Class and Preferred Term - Part 1
Safety Set

System Organ Class Preferred Term	Number of Events / Subjects (%)			
	COHORT 1 (Dose xx mg/ml) (N=x)	COHORT 2 (Dose xx mg/ml) (N=x)	Overall (N=x)
Any TEAEs	x / x (x.x)	x / x (x.x)	x / x (x.x)	x / x (x.x)
<SYSTEM ORGAN CLASS TERM> <PREFERRED TERM> <PREFERRED TERM>	x / x (x.x) x / x (x.x)	x / x (x.x) x / x (x.x)	x / x (x.x) x / x (x.x)	x / x (x.x) x / x (x.x)
<SYSTEM ORGAN CLASS TERM> <PREFERRED TERM> <PREFERRED TERM> <PREFERRED TERM> <PREFERRED TERM>	x / x (x.x) x / x (x.x) x / x (x.x) x / x (x.x) x / x (x.x)	x / x (x.x) x / x (x.x) x / x (x.x) x / x (x.x) x / x (x.x)	x / x (x.x) x / x (x.x) x / x (x.x) x / x (x.x) x / x (x.x)	x / x (x.x) x / x (x.x) x / x (x.x) x / x (x.x) x / x (x.x)

Source Listing: 16.2.8.1; Produced: yyyy-mm-ddThh:mm - Page x of y
A subject is counted only once per system organ class and preferred term.
Percentages will be calculated from the number of subjects in the Safety Set within a cohort.
MedDRA version <x.x>.

Programming note: A similar table will be presented for Part 2, with the column headers for each of the 3 groups

OMO-103-01
Table 14.3.1.2a
Summary of Treatment Emergent Adverse Events by System Organ Class and Preferred Term - Event Count - Part 1
Safety Set

System Organ Class Preferred Term	Number of Events (%)			Overall (N=x)
	COHORT 1 (Dose xx mg/ml) (N=x)	COHORT 2 (Dose xx mg/ml) (N=x)	
<SYSTEM ORGAN CLASS TERM>				
<PREFERRED TERM>	x (x.x)	x (x.x)	x (x.x)	x (x.x)
<PREFERRED TERM>	x (x.x)	x (x.x)	x (x.x)	x (x.x)
<SYSTEM ORGAN CLASS TERM>	x (x.x)	x (x.x)	x (x.x)	x (x.x)
<PREFERRED TERM>	x (x.x)	x (x.x)	x (x.x)	x (x.x)
<PREFERRED TERM>	x (x.x)	x (x.x)	x (x.x)	x (x.x)
<PREFERRED TERM>	x (x.x)	x (x.x)	x (x.x)	x (x.x)
<PREFERRED TERM>	x (x.x)	x (x.x)	x (x.x)	x (x.x)

Source Listing: 16.2.8.1; Produced: yyyy-mm-ddThh:mm - Page x of y
Percentages will be calculated from the number of events in the Safety Set within a cohort.
MedDRA version <x.x>.

Programming note: A similar table will be presented for Part 2, with the column headers for each of the 3 groups

OMO-103-01
Table 14.3.1.3
Summary of Treatment Emergent Adverse Events by Preferred Term - Part 1
Safety Set

Preferred Term	Number of Events / Subjects (%)			
	COHORT 1 (Dose xx mg/ml) (N=x)	COHORT 2 (Dose xx mg/ml) (N=x)	Overall (N=x)
Any TEAEs	x / x (x.x)	x / x (x.x)	x / x (x.x)	x / x (x.x)
<PREFERRED TERM>	x / x (x.x)	x / x (x.x)	x / x (x.x)	x / x (x.x)
<PREFERRED TERM>	x / x (x.x)	x / x (x.x)	x / x (x.x)	x / x (x.x)
<PREFERRED TERM>	x / x (x.x)	x / x (x.x)	x / x (x.x)	x / x (x.x)
<PREFERRED TERM>	x / x (x.x)	x / x (x.x)	x / x (x.x)	x / x (x.x)
<PREFERRED TERM>	x / x (x.x)	x / x (x.x)	x / x (x.x)	x / x (x.x)

Source Listing: 16.2.8.1; Produced: yyyy-mm-ddThh:mm - Page x of y
 A subject is counted only once per preferred term.
 Percentages will be calculated from the number of subjects in the Safety Set within a cohort.
 MedDRA version <x.x>.

Programming note: A similar table will be presented for Part 2, with the column headers for each of the 3 groups

OMO-103-01
Table 14.3.1.4
Summary of Treatment Emergent Adverse Events by Grade, System Organ Class and Preferred Term- Part 1
Safety Set

<GRADE X>

System Organ Class Preferred Term	Number of Events / Subjects (%)			
	COHORT 1 (Dose xx mg/ml) (N=x)	COHORT 2 (Dose xx mg/ml) (N=x)	Overall (N=x)
<SYSTEM ORGAN CLASS TERM>	x / x (x.x)	x / x (x.x)	x / x (x.x)	x / x (x.x)
<PREFERRED TERM>	x / x (x.x)	x / x (x.x)	x / x (x.x)	x / x (x.x)
<PREFERRED TERM>	x / x (x.x)	x / x (x.x)	x / x (x.x)	x / x (x.x)
<PREFERRED TERM>	x / x (x.x)	x / x (x.x)	x / x (x.x)	x / x (x.x)
<SYSTEM ORGAN CLASS TERM>	x / x (x.x)	x / x (x.x)	x / x (x.x)	x / x (x.x)
<PREFERRED TERM>	x / x (x.x)	x / x (x.x)	x / x (x.x)	x / x (x.x)
<PREFERRED TERM>	x / x (x.x)	x / x (x.x)	x / x (x.x)	x / x (x.x)
<PREFERRED TERM>	x / x (x.x)	x / x (x.x)	x / x (x.x)	x / x (x.x)

Source Listing: 16.2.8.1; Produced: yyyy-mm-ddThh:mm - Page x of y
A subject is counted only once per system organ class, preferred term and severity.
Percentages will be calculated from the number of subjects in the Safety Set within a cohort.
MedDRA version <x.x>.

Programming note: A similar table will be presented for Part 2, with the column headers for each of the 3 groups

OMO-103-01
Table 14.3.1.5

Summary of Treatment Emergent Adverse Events by Relationship to IMP, System Organ Class and Preferred - Part 1 Safety Set

<RELATIONSHIP>

System Organ Class Preferred Term	Number of Events / Subjects (%)			
	COHORT 1 (Dose xx mg/ml) (N=x)	COHORT 2 (Dose xx mg/ml) (N=x)	Overall (N=x)
<SYSTEM ORGAN CLASS TERM>	x / x (x.x)	x / x (x.x)	x / x (x.x)	x / x (x.x)
<PREFERRED TERM>	x / x (x.x)	x / x (x.x)	x / x (x.x)	x / x (x.x)
<PREFERRED TERM>	x / x (x.x)	x / x (x.x)	x / x (x.x)	x / x (x.x)
<SYSTEM ORGAN CLASS TERM>	x / x (x.x)	x / x (x.x)	x / x (x.x)	x / x (x.x)
<PREFERRED TERM>	x / x (x.x)	x / x (x.x)	x / x (x.x)	x / x (x.x)
<PREFERRED TERM>	x / x (x.x)	x / x (x.x)	x / x (x.x)	x / x (x.x)

Source Listing: 16.2.8.1; Produced: yyyy-mm-ddThh:mm - Page x of y

A subject is counted only once per system organ class, preferred term and relationship.

Percentages will be calculated from the number of subjects in the Safety Set within a cohort.

MedDRA version <x.x>.

